13.2 STATISTICAL METHODS

13.2.1 Analysis populations

Patients without a valid or adequately obtained Informed Consent Form (ICF) will be excluded from any analysis population.

The following analysis populations have been defined for these statistical analyses:

- Safety: All randomized patients who took at least one dose of study product.
- Intention to treat (ITT): All randomized patients who took at least one dose of study product and have at least baseline and one post-baseline assessment of the primary efficacy variable. Patients who interrupt treatment will be considered as “failures” for qualitative variables and their missing quantitative data will be substituted according to the LOCF method (Last Observation Carried Forward).
- Per protocol (PP): All randomized patients who completed Period I and did not have significant protocol violations that regard inclusion/exclusion criteria or can condition the efficacy evaluation.

The efficacy analysis will be performed on the ITT population and also on the PP population as a supportive analysis for the primary endpoint and reported overall and by planned treatment group. Safety will be evaluated in the Safety population and reported overall and by actual treatment group.

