11.2.3 Handling of patients after permanent treatment discontinuation

Patients will be followed-up according to the study procedures as specified in this protocol up to the scheduled date of study completion, or up to recovery or stabilization of any AE, whichever comes last.

If possible, and after the permanent discontinuation of treatment, the patients will be assessed using the procedures normally planned for the last visit.

All cases of permanent treatment discontinuation should be recorded by the Investigator in the CRF when considered as confirmed.

For patients who fail to return to the site, the Investigator should make the best effort to re-contact the patient's parents and to determine their child's health status. Attempts to contact such patients must be documented in the patient's records.

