13.1 DETERMINATION OF SAMPLE SIZE

160 patients are to be enrolled in this study.

Confidential

A sample of 72 patients for each group will have an 80% power to detect an effect size on the primary variable ($\delta = |\mu_1 - \mu_2| / \sigma$) of 0.47 (medium effect size) (12), using an independent samples t-test with a two-tailed significance level of 5%.

A sample size of 80 patients per group will account for an expected dropout rate of 12% (13), using Freedman's formula (*Control Clin Trials*, 1990): $n' = 100 * n / 100 - x$, where x is the expected dropout rate.

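### Carrying Week 2 TSS forward to Week 4, and leaving patients with no post-baseline TSS out of the ITT set, can bias the primary comparison if dropout or symptom course differs by arm

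*Combined protocol and SAP*

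**What the plan says.** The primary endpoint is change in TSS from baseline to Week 4, compared by a t-test or a non-parametric analogue (13.2.2). Under 10.1.1 and the assessment chart in section 2, TSS is recorded at Visits 2, 3 and 4 only, that is Weeks 0, 2 and 4.

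For patients who interrupt treatment, 13.2.1 states that "their missing quantitative data will be substituted according to the LOCF method". The synopsis and 13.2.2 repeat the rule. To enter the ITT set a patient must have taken study product and must "have at least baseline and one post-baseline assessment of the primary efficacy variable". The one supportive analysis of the primary endpoint uses the per-protocol set, which is confined to patients who finished Period I without important violations.

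Section 11.2.3 opens by planning follow-up after permanent discontinuation through to the scheduled end of study. It adds that, where possible, "the patients will be assessed using the procedures normally planned for the last visit". The plan does not say whether TSS values collected after discontinuation are used. It gives no rule for a missing Week 4 TSS in a patient who did not interrupt treatment. Section 13.2.2 defers further detail to a separate SAP, whose text is not among the documents supplied.

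**The concern.** LOCF assumes that a child who leaves after Week 2 would have had the same score at Week 4. The plan does not justify this, and the score itself makes it doubtful. Overall TSS is the mean of a 12-hour and a two-week recall score. At Week 2 the longer recall covers Weeks 0 to 2, and at Week 4 it covers Weeks 2 to 4. LOCF therefore puts an earlier, non-overlapping window in place of the one that the endpoint is about.

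The carried value is then analysed as if observed. Patients lost before Week 2 disappear from the analysis, although the set is called ITT. Both rules act on events after randomisation, so the protection of randomisation is lost if those events, or the symptom course around them, differ by arm. What is at stake is the estimate and the error rates of the primary test.

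**Working it through.** **Inputs from the documents (13.1, 9.4, 10.1.1).** Two-sided 5% level, 80% power, standardised effect 0.47, 72 evaluable per group, 160 enrolled 1:1, 12% expected dropout with no split by arm or timing, TSS at Weeks 0, 2 and 4. No raw SD and no TSS course are given.

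**1. The plan's own figure.** Section 13.1 says "A sample of 72 patients for each group will have an 80% power to detect an effect size on the primary variable" of 0.47.
- Normal approximation: 2 × (1.960 + 0.842)² / 0.47² = 71.1, rounded up to 72.
- The noncentral t solution is 72.04, with power of 79.98% at 72. The figure is reproduced.
- Dropout inflation: 72 / 0.88 = 81.8, so 82 against the stated 80 (72 / 0.90 = 80). This small gap does not affect the present point.
- Expected dropouts: 0.12 × 160 = 19.2, about 19 patients.

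**2. LOCF bias by hand.** Let d be the proportion of an arm lost after Week 2 and g the further mean improvement that those patients would have had by Week 4. LOCF shifts the arm mean by d × g. With the same g in both arms, bias = (difference in d) × g. Assumed dropout splits and gains, with an assumed SD of 5.5:
- (0.09 − 0.03) × 2 = 0.12 points; 0.12 / 5.5 = 0.022 SD, 5% of 0.47.
- (0.15 − 0.05) × 3 = 0.30 points; 0.055 SD, 12% of 0.47.
- (0.15 − 0.05) × 4 = 0.40 points; 0.073 SD, 15% of 0.47.

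With equal dropout, only the part of the treatment effect that arises after Week 2 is lost. Take 12% dropout, a quarter of it before Week 2 (d = 0.09), and 30% or 50% of the effect after Week 2. The attenuation is 0.09 × 0.30 × 0.47 = 0.013 SD or 0.09 × 0.50 × 0.47 = 0.021 SD.

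**3. Simulation.** 4000 runs per scenario, 80 per arm. Assumptions not in the documents: Week 4 SD 1; Week 2 SD 0.8 or 1.0; Week 2 to Week 4 correlation 0.6; placebo change −1 SD; 30% or 50% of improvement after Week 2; a quarter of dropouts with no post-baseline TSS; dropout unrelated to Week 2 response or more likely when it is poor (logit slope 1). The comparator is a likelihood estimator valid when data are missing at random (MAR), which uses Week 2 to inform Week 4. Negative bias favours the product.

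| True effect | Dropout, product / placebo | LOCF bias (SD) | LOCF rejects | Likelihood rejects |
|---|---|---|---|---|
| 0 | 12% / 12% | 0.005 to 0.006 | 5.1–5.3% | 5.0–5.2% |
| 0 | 4% / 20% | −0.075 to −0.033 | 5.9–7.6% | 5.3% |
| 0 | 20% / 4% | 0.044 to 0.060 | 5.5–6.4% | 4.9% |
| 0.47 | 12% / 12% | 0.018 to 0.027 | 72.1–78.6% | 79.4% |
| 0.47 | 4% / 20% | −0.045 to −0.029 | 86.6–87.1% | 75.8% |
| 0.47 | 20% / 4% | 0.066 to 0.083 | 63.2–68.2% | 80.8% |

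The 50% share was run only for the second and fourth rows, so 0.083 is not an upper bound. Monte Carlo error is about 0.167 / √4000 = 0.003 SD for a mean and √(0.05 × 0.95 / 4000) = 0.3 percentage points for a 5% rate. The 0.005 to 0.006 in the first row is noise: the likelihood estimator shows 0.006 to 0.007 in the same runs. Some of that noise is also in the fourth row, which is why it lies slightly above the hand figures of 0.013 and 0.021.

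**4. Standard error.** In every scenario the mean t-test SE under LOCF agreed with the empirical SD of the LOCF estimate to within 0.002. The LOCF SE was 0.158 to 0.171 against 0.166 to 0.167 for the likelihood estimator: 0.158 / 0.166 = 0.95 and 0.171 / 0.166 = 1.03, so from about 5% smaller to 3% larger.

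**5. Patients with no post-baseline TSS.** With unequal dropout the likelihood estimator still missed the true value by 0.01 to 0.02 SD, because these patients remained excluded.

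**The case against.** The strongest case for the plan is that the effect is modest. With equal dropout, type I error stays near 5% and the bias at the design effect is conservative. Larger figures need an assumed dropout imbalance. That stands, and it limits how serious the point is.

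Four further replies carry weight.
- The per-protocol set is restricted to Period I completers, so it does replace the LOCF assumption with another. This is correct, but a completers analysis also conditions on post-randomisation events and removes protocol violators, so it is a weak check.
- The LOCF wording covers missing data in patients who interrupt treatment. On a plain reading, a Week 4 TSS observed under the follow-up in the first sentence of 11.2.3 is not missing and would not be overwritten. The plan does not say so, however. The later sentence, "the patients will be assessed using the procedures normally planned for the last visit", does not settle it: the last visit is Visit 5 or 6, where TSS is not scheduled.
- A separate SAP is announced and may add sensitivity analyses. What can be said is that none beyond the per-protocol analysis appears in the documents supplied.
- Section 13.2.2 requires disposition and reasons for exclusion from each set to be reported, so omissions from the ITT set will be visible. Reporting them does not remove any bias that they cause.

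A reader might also infer that LOCF necessarily understates the standard error. Step 4 of the working does not support that: the SE tracked the estimator's own variability and lay on either side of the MAR-based one. Where type I error rose, the main cause was bias under unequal dropout. Nor do the documents show that LOCF works against a particular arm. Both arms take an antihistamine throughout Period I, so further improvement after Week 2 is plausible, but no TSS course is given.

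**Conclusion.** The point holds in a limited form. The plan prescribes LOCF for the primary endpoint in patients who interrupt treatment and leaves out randomised patients with no post-baseline TSS. Either rule can bias the Week 4 comparison if dropout or symptom course differs by arm, and single imputation does not carry the uncertainty of the missing values.

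Taking the hand calculation and the simulation together, markedly unequal dropout gives a bias of about 0.02 to 0.08 SD in either direction. The simulated type I error in those cases was 5.5 to 7.6%. With 12% in both arms there is no material bias under the null and an attenuation of 0.02 to 0.03 SD at 0.47, with simulated power of 72.1 to 78.6% against 79.4% for a likelihood analysis. All of this rests on assumed dropout splits, symptom course, SD and correlation. The only related figure in the documents is the 12% overall. The rule should be changed because a better one is cheap, not because a large bias has been shown.

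**What to change.** Make the primary analysis a mixed model for repeated measures of TSS change at Weeks 2 and 4, with treatment, visit, treatment by visit, baseline TSS and allergy type. The Week 4 treatment contrast is primary, and no values are carried forward. Also:
- Analyse all randomised patients with valid consent by assigned arm, with multiple imputation for those who have no post-baseline TSS. Imputation under MAR keeps these patients in the analysis, but it cannot correct for loss that depends on unobserved scores.
- State that a Week 4 TSS observed after treatment discontinuation, under the follow-up in the first sentence of 11.2.3, is used as observed. This makes the estimand for discontinuation explicit.
- Add one delta-adjusted sensitivity analysis, to show how far the result depends on the missing-at-random assumption.
- Keep LOCF, if wanted, only as a sensitivity analysis.

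The cost is SAP wording and modest programming, settled before database lock. No visits or assessments are added. The drawback is an analysis that is slightly harder to explain than a t-test.

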13.2.2 Statistical Analysis

All data collected in the study will be listed and summarized as appropriate as described below. Continuous data will be summarized by means of common descriptive statistics: mean, standard deviation (SD), median, first and third quartiles, minimum and maximum. Categorical data will be presented by absolute and relative frequencies (n and %) or contingency tables.

For the safety analysis, patients will be included in based on available assessments; no missing data handling approach will be applied. For efficacy analyses, patients who interrupt treatment will be considered as “failures” for qualitative variables and their missing quantitative data will be substituted according to the LOCF method (Last Observation Carried Forward). Unless stated otherwise, two-sided p-values <0.05 will be considered statistically significant.

All statistical tables, listings, figures and analyses will be generated using SAS® release 9.4 or later (SAS Institute Inc., Cary NC, USA).

No interim analyses are planned.

Further details about data analysis will be provided in the Statistical Analysis Plan document.

All data about patient demographics and baseline characteristics will be summarized on the ITT population by treatment group by means of summary descriptive statistics.

The number and percentages of subjects meeting all eligibility criteria at screening will be provided. The analysis populations will be described and the reasons for excluding a patient from any particular population will be provided with the number of protocol deviators per each criterion.

A complete description of patients’ disposition will be provided specifying the number of randomized patients, the number of patients at each visit, the number of completed and discontinued patients and the reason for the discontinuation.

Medical history data will be presented by Medical Dictionary for Regulatory Activities MedDRA dictionary system organ class (SOC) and preferred term (PT).

Concomitant medications and significant non-drug therapies will be presented by WHO Drug Dictionary ATC class and preferred term.

- **Primary endpoint**

Changes from baseline of TSS scores will be calculated after 4 weeks of treatment. The between-group analysis will be performed by means of a t-test for independent samples or analogous non-parametric test.

- **Secondary endpoints**

- Change from baseline of VAS score after 2 and 4 weeks of treatment. The between-group analysis will be performed by means of a t-test for independent samples or analogous non-parametric test.

- Changes from baseline of TSS scores after 2 weeks of treatment. The between-group analysis will be performed by means of a t-test for independent samples or analogous non-parametric test.
 - Changes from baseline of TSS score for each patient after 2 and 4 weeks of treatment will be classified as $\geq 30\%$ and $< 30\%$, thus defining responder and non-responder patients. Between-group differences will be tested by means of a Chi-square test with 2x2 contingency tables.
 - Time to maximum effect on TSS vs placebo will be analysed by means of t-test for independent samples after log-transformation of the data or analogous non-parametric test.
 - Between-group differences in the number of patients using rescue treatment will be analyzed by means of a Chi-square test with 2x2 contingency tables.
 - Changes from baseline in TNSS, TOSS and TTSS scores will be calculated after 2 and 4 weeks of treatment and between-group differences analyzed by means of a t-test for independent samples or analogous non-parametric test.
 - The number of patients with score for a single symptom ≤ 1 will be calculated and the between-group differences analyzed by means of a Chi-square test with 2xn contingency tables, where n represents the number of observations.
 - The intensity of the onset of exacerbations occurring during Period II will be evaluated through the TTS score and compared between the two groups using a t-test for independent samples or analogous non-parametric test.
 - The between-group differences in the number and duration of exacerbations occurring during Period II will be analyzed by means of a Mann-Whitney U test.
- **Quality of life**

Changes from baseline of the PRQLQ total score will be calculated at the end of Period I (Week 4) and end of Period II (Week 8 or Week16). An analysis of variance for repeated measures will be adopted, isolating the variability due to type of allergy, treatment group, time of observation and their interaction.

- **Safety**

All safety analyses will be performed on the Safety set. No missing data handling approach will be applied.

Results of physical examinations at each assessment will be presented.

The incidence of Adverse Events (AEs) and Serious Adverse Events (SAEs) recorded throughout the study will be presented overall and by treatment group respectively.

According to the onset date of the event, AEs will be defined as follows:

- treatment-emergent AE, those events with an onset date after any treatment initiation
- non-treatment-emergent AE, those events with an onset date between informed consent and any treatment initiation

Nontreatment-emergent AEs will be listed only.

Treatment-emergent AEs will be summarized by MedDRA dictionary system organ class and preferred term. A summary of treatment-emergent AEs by preferred term and severity will be also provided. All related treatment-emergent AEs, treatment-emergent AEs with an outcome of death, treatment-emergent AEs leading to discontinuation of treatment will be summarized by MedDRA dictionary system organ class and preferred term and will also be listed. Serious treatment-emergent AEs will be summarized similarly.

All deaths occurred will be listed together with all their details.

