6 STUDY OBJECTIVES

6.1 PRIMARY

The primary objective of the study is to evaluate the effect of Lertal[®] as add on therapy in pediatric patients with allergic rhinoconjunctivitis, using Total Symptom Score (TSS) as primary variable. The primary endpoint of this study is the change from baseline of the TSS after 4 weeks of treatment.

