7 STUDY DESIGN

7.1 DESCRIPTION OF THE PROTOCOL

❖ Run-in

The 2-week run-in period consists of two visits: Visit 1 at Week -2 and Visit 2 at Week 0. Visit 1 and Visit 2 may be performed on the same day. During these visits, after having obtained signed informed consent from the patient, the Investigator will gather demographic and medical history data, perform a physical examination of the patients and evaluate their eligibility for the study according to inclusion/exclusion criteria indicated in [Section 8](#). Eligible patients will then be randomized in a 1:1 ratio into two treatment groups and will be dispensed one of the study treatments:

- Lertal® double-layer tablets (1 tab/day for 4 weeks) plus standard therapy (antihistamine).

or

- Lertal® placebo tablets (1 tab/day for 4 weeks) plus standard therapy (antihistamine).

The randomization list will be stratified by type of allergy (pollen or dust mites).

Baseline assessments of patient reported outcomes (PRO) will be collected at Visit 2 (Week 0). The patient will also be given a diary on which to record the use of rescue medication/concomitant medication and the occurrence of adverse events. The diary will also be used to record the occurrence/duration of exacerbations during Period II (need of an antihistamine medication of any kind, at any dose and of any duration).

❖ Period I

Visit 3 (Week 2) and Visit 4 (Week 4) constitute the 4-week double-blinded treatment period (Period I). During these visits, patients will be asked to complete their questionnaires and to return their diaries so information concerning safety (adverse events) and the use of rescue/concomitant medications can be collected. Patients need to return all unused product at both visits to check compliance with treatment. Once all data entry related to Period I has been completed (the Investigator has to certify that the data entered are complete and accurate), the eCRF will make the unblinding procedure available to the investigator so he or she can find out what treatment was

taken by the patient during the double-blinded period. All assessments scheduled for Visit 4 shall be performed prior to unblinding.

A patient that concludes treatment Period I and still presents symptoms that do not permit interruption of standard therapy is considered a non-responder and will not take part in Period II of the study. The patient will be discontinued from the study.

❖ Period II

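### At least 17 to 18 secondary comparisons fall under an unqualified p<0.05 significance rule, with no multiplicity control, gate on the primary result or exploratory label

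*Combined protocol and SAP*

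**What the plan says.** Section 6.1 names one endpoint at one time point: "The primary endpoint of this study is the change from baseline of the TSS after 4 weeks of treatment". Section 13.1 sizes the trial on that variable alone, with a two-sided 5% t-test: "A sample of 72 patients for each group will have an 80% power to detect an effect size on the primary variable", the effect being 0.47 standard deviations.

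Section 13.2.2 gives the only significance rule in the document: "Unless stated otherwise, two-sided p-values <0.05 will be considered statistically significant". The same section then assigns a between-group test to each secondary endpoint listed in section 6.2. One bullet can cover several tests; for example, "Changes from baseline in TNSS, TOSS and TTSS scores will be calculated after 2 and 4 weeks of treatment" is six comparisons.

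Nothing in the text takes the secondary tests out of the general rule. No hierarchy, alpha adjustment or condition on the primary result is given, and no statement that secondary results are exploratory. Section 13.2.1 does describe one analysis as supportive, but that is the per-protocol analysis of the primary endpoint. Section 13.2.2 also says that further analysis details will follow in a separate Statistical Analysis Plan.

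**The concern.** A rule that calls every p-value below 0.05 significant, applied to a long list of secondary tests, makes a chance finding far more probable than the nominal level suggests. If the Week 4 TSS comparison were not significant, nothing in this text would stop a report from describing one or more secondary results as statistically significant on the same terms as the primary.

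Some of those results would come from Period II, which compares open-label Lertal with no treatment, after investigators can learn the allocation and after Period I non-responders have left (section 7.1). What is at stake is how far the secondary results can be relied on, not the primary conclusion.

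**Working it through.** **The plan's own figure.** Sample size for a two-sample comparison (section 13.1: effect 0.47, two-sided 5%, power 80%): n = 2(1.960 + 0.842)² / 0.47² = 71.1, so 72 per group, as stated. With 72 per group, power is 80.5% by the normal approximation and 79.98% by the noncentral t. This calculation covers the primary test only. The plan states no family-wise error rate for the secondary endpoints, so there is no figure of that kind to reproduce.

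**Count of secondary tests (section 13.2.2).**
- VAS, Weeks 2 and 4: 2
- TSS, Week 2: 1
- TSS responders, Weeks 2 and 4: 2
- Time to maximum effect: 1
- Rescue use: 1
- TNSS, TOSS and TTSS, Weeks 2 and 4: 6
- Single-symptom score of 1 or less: 1
- Exacerbation intensity, number and duration: 3
- PRQLQ: 1

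Total: 2 + 1 + 2 + 1 + 1 + 6 + 1 + 3 + 1 = 18.

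The total is 17 if exacerbation intensity cannot be run. That test needs a symptom score, and the assessment chart in section 2 schedules none at Visits 5 and 6. The total rises if rescue is tested in each period (section 9.10 defines it differently in each), if the PRQLQ is tested by visit or by model term, or if the nine symptoms are tested separately.

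**Independent tests, no effect anywhere.**
- Either direction, 18 tests: 1 − 0.95^18 = 60.3%
- Favouring Lertal, 18 tests: 1 − 0.975^18 = 36.6%
- With 17 tests: 58.2% and 35.0%
- Expected false positives among 18: 18 × 0.05 = 0.9, of which 18 × 0.025 = 0.45 favour Lertal

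**Correlated tests.** The documents give no correlations, so a range is assumed. Each test statistic was simulated as Z = √ρ·C + √(1−ρ)·E, with C common to all 18 and E specific to each (200,000 draws, critical value 1.96). In the last row the primary statistic was added as a nineteenth with the same correlation.

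| Common correlation ρ | 0 | 0.3 | 0.5 | 0.7 |
|---|---|---|---|---|
| At least one significant, either direction | 60% | 51% | 40% | 28% |
| At least one significant, favouring Lertal | 37% | 26% | 20% | 14% |
| At least one favouring Lertal while the primary does not significantly favour it | 35.6% | 24.5% | 18.0% | 11.6% |

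Independence is a ceiling here, not a central case. At least 10 of the 18 tests are built from TSS or its components (TSS Week 2, responders at two visits, time to maximum effect, six sub-score tests), and section 10.1.1 defines TSS as the sum of the three sub-scores.

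An illustrative patient-level simulation with 72 per arm and three assumed correlation structures (3,000 trials each) gave 46% to 51% in either direction and 25% to 27% favouring Lertal, inside the ranges above.

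**Effect of a remedy.** If secondary tests may be declared only after a significant primary, the chance of any false secondary claim when Lertal does nothing cannot exceed 5% in either direction or 2.5% in Lertal's favour. The simulated values are 3.0% to 4.4% and 0.9% to 2.2% for ρ from 0 to 0.7. For comparison, Bonferroni over 18 tests uses 0.05/18 = 0.0028 each and gives 4.9% if independent. A gate alone does not control error among the secondaries when the primary effect is real; that also needs a fixed order or a method such as Holm.

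**The case against.** The strongest defence is that these endpoints are labelled secondary, that secondary endpoints are conventionally read as supportive, and that the p<0.05 sentence is only a general reporting threshold. No section says that a secondary result can establish efficacy or make up for a failed primary. This stands in part: permission to claim efficacy whatever the primary shows is inferred from silence and is not a written rule. But the plan does define significance for the secondary tests and does not write the convention down.

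Second, the separate Statistical Analysis Plan may contain a testing rule. If it does, the point falls away. On the text reviewed, the general rule applies without qualification.

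Third, the 60% figure assumes independence and counts results favouring placebo. Both criticisms are right. A reader might infer from it that a false efficacy claim is likely even if Lertal does nothing. The figures do not support that: for 18 tests, the chance of a false result favouring Lertal is below one half even under independence.

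Fourth, a reader might infer that the trial's main error rate is inflated. It is not, because there is one primary endpoint, at one time point, tested once at two-sided 5%.

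Finally, the Period II comparisons are open-label and exclude Period I non-responders, so they may not hold a 5% level in the first place. That is a question of bias, which multiplicity control does not cure.

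**Conclusion.** The point holds as a gap in the control and labelling of secondary results. At least 17 to 18 comparisons fall under an unqualified p<0.05 rule. With 18 tests and no treatment effect, the chance of at least one false positive favouring Lertal is at most about 37%, and 14% to 26% at assumed correlations of 0.7 down to 0.3. That is roughly 6 to 15 times the nominal 2.5%. In either direction the ceiling is about 60%, with 28% to 51% over the same correlations.

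These figures assume that each test holds its 5% level, that correlations are not negative, that the count is 18, and that no rule in the separate Statistical Analysis Plan says otherwise. The primary test is unaffected. This is a low-cost improvement to what may be concluded from the secondary endpoints, not a flaw in the main comparison.

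**What to change.** State in section 13.2.2 and in the Statistical Analysis Plan that only the Week 4 TSS comparison is confirmatory. State also that all secondary results, including every open-label Period II result, are supportive and will be reported as estimates with 95% confidence intervals and nominal p-values.

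If the sponsor wants claims from secondary endpoints, pre-specify a short fixed order of Period I endpoints of its own choosing. Test them only after a significant primary result, each at two-sided 5%, and stop at the first that is not significant.

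The cost is a few sentences of text and fewer secondary results that can be called significant. Sample size, visits and data collection do not change. The bias in the Period II comparisons remains and needs separate treatment.
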